## 7. ETHICAL CONSIDERATIONS

**Recruitment and Selection of Participants:** Recruitment will commence following ethical approval from the University of Sydney Human Research Ethics Committee. A recruitment flyer (appendix D) targeting parents of children with ASD that have behaviours related to sensory processing will be distributed to ASD support groups, including Autism Community Network, and Sutherland Autism Support Group.

Potential participants will be required to contact the researchers by email if they are interested to participate. When contacted, the researchers will send the participants a parent and child Participant Information Statement (PIS; appendix E) to explain the purpose of the study. The researchers will ask the participants to read child and parent PIS and email back their contact details if they are interested in participating. The researchers will phone interested participants to ensure they are eligible for the study and organise a home visit.

**Informed Consent:** During the first home visit, the researcher will explain the consent process to the participants. The parent and child will sign the consent form (appendix F) if they are willing to participate.

**Confidentiality and Privacy:** Pseudonyms will be used for all participants in all documents to protect identity.

**Data storage and Record Retention:** All electronic materials will be stored in password protected file in Research Data Store (RDS) available through the University of Sydney. Any hard copy materials will be scanned in RDS and shredded. Only researchers will know the passwords for RDS. All materials will be kept in RDS for 20 years or until participants (children) are 25 years old.

## 8. SAFETY CONSIDERATIONS

Parents may experience negative reactions when discussing their child’s undesirable behaviours. If this occurs, the researchers will ensure the parents have access to a support person (family member, friend, psychologist) they can talk with. There is a low risk that the proprioceptive activities could cause injury to parents or children. To minimise risk the activities will be individually tailored to the child and parent capacities and will be similar to activities they already participate in at home (but with an added proprioceptive element).

## 9. OUTCOMES AND SIGNIFICANCE

The study hopes to support occupational therapists with how to use sensory-based intervention with families. Specifically, the research aims to provide preliminary evidence for using proprioceptive activities to improve undesirable behaviours of children with ASD and co-occurring sensory over-responsiveness. Furthermore, by adopting a real-world, parent-friendly intervention, the study has the potential to be easily replicated within households of families with children with ASD.

## 10. TIMELINES / MILESTONES

**Timeline** (July 2017 – July 2018)

Date	Phase	Participant Tasks	Researcher Tasks
July 18 th	Ethics approval	
 
○ N/a
 
	
 
○ Submit ethics
 

< August 13 th	Preparation - find potential participants	
 
○ Email interest
 
	
 
○ Distribute flyer
 
○ Phone potential participants to ensure they meet eligibility criteria
 

< August 13 th	Preparation – screen potential participants	
 
○ Read PIS and consent form – ask questions
 
○ Complete Sensory Profile 2 online
 
	
 
○ Email PIS and consent form – answer questions
 
○ Email Sensory Profile 2 Online
 

< August 13 th	Preparation – recruit eligible participants	
 
○ Parent and child sign consent form
 
	
 
○ Formulate target behaviour and outcome measure (see below)
 
○ Set up PIEL Survey (specific to each family)
 

August 14 th - August 27 th	Phase A1 (2 weeks)	
 
○ Parent scores behaviour daily
 
	
 
○ No home visits (unless need support to use PIEL Survey)
 

August 28 th – October 1 st	Phase B (5 weeks)	
 
○ Parent implements proprioceptive activities as per individual family plan (see below)
 
○ Parent scores behaviour daily
 
	
 
○ Provide education to family (see handout below)
 
○ Create individual family plan (see below)
 
○ Home visits 1/week
 

October 2 nd – October 15 th	Phase A2 (2 weeks)	
 
○ Parent scores behaviour daily
 
	
 
○ Reminder to participant to stop all proprioceptive intervention
 
○ No home visits
 

October 15 th – November 19 th	Conclusion	
 
○ Parents email all data
 
	
 
○ Follow up / thank you phone call
 
○ Visual analysis
 
○ Send lay summary to participants
 

January – July 2018	Research article	
 
○ n/a
 
	
 
○ Prepare and publish research article
 

## 11. FINANCIAL

This study has no funding or grants.

## 12. PUBLICATION POLICY / DISSEMINATION OF RESULTS

Participants will receive a lay summary of the results. The results will be published in a journal article by [name] and [name].

## 14. APPENDICES

## Appendix A

### Sensory Profile 2 Child (online administration)

**Instructions:** The screens that follow contain statements that describe how children may act. Please read each phrase and select the option that best describes how often your child shows these behaviors. Please mark one option for every statement.

**Use these guidelines to mark your responses.**

When presented with the opportunity, my child...

responds in this manner **Almost Always** (90% or more of the time)

responds in this manner **Frequently** (75% of the time)

responds in this manner **Half the Time** (50% of the time)

responds in this manner **Occasionally** (25% of the time)

responds in this manner **Almost Never** (10% or less of the time)

If you are unable to answer because you have not observed the behavior or believe it does not apply to your child, please click **Does Not Apply**.

## AUDITORY Processing

My child...

1. reacts strongly to unexpected or loud noises (for example, sirens, dog barking, hair dryer)

Almost Always  Frequently  Half the Time  Occasionally  Almost Never  Does Not Apply

2. holds hands over ears to protect them from sound

Almost Always  Frequently  Half the Time  Occasionally  Almost Never  Does Not Apply

3. struggles to complete tasks when music or TV is on

Almost Always  Frequently  Half the Time  Occasionally  Almost Never  Does Not Apply

4. is distracted when there is a lot of noise around

Almost Always  Frequently  Half the Time  Occasionally  Almost Never  Does Not Apply

5. becomes unproductive with background noise (for example, fan, refrigerator)

Almost Always  Frequently  Half the Time  Occasionally  Almost Never  Does Not Apply

6. tunes me out or seems to ignore me

Almost Always  Frequently  Half the Time  Occasionally  Almost Never  Does Not Apply

7. seems not to hear when I call his or her name (even though hearing is OK)

Almost Always  Frequently  Half the Time  Occasionally  Almost Never  Does Not Apply

8. enjoys strange noises or makes noise(s) for fun

Almost Always  Frequently  Half the Time  Occasionally  Almost Never  Does Not Apply

Comments (optional):

**VISUAL Processing**

**My child...**

**9. prefers to play or work in low lighting**

**Almost Always Frequently Half the Time Occasionally Almost Never Does Not Apply**

**10. prefers bright colors or patterns for clothing**

**Almost Always Frequently Half the Time Occasionally Almost Never Does Not Apply**

**11. enjoys looking at visual details in objects**

**Almost Always Frequently Half the Time Occasionally Almost Never Does Not Apply**

**12. needs help to find objects that are obvious to others**

**Almost Always Frequently Half the Time Occasionally Almost Never Does Not Apply**

**13. is more bothered by bright lights than other same-aged children**

**Almost Always Frequently Half the Time Occasionally Almost Never Does Not Apply**

**14. watches people as they move around the room**

**Almost Always Frequently Half the Time Occasionally Almost Never Does Not Apply**

**15. is bothered by bright lights (for example, hides from sunlight through car window)**

**Almost Always Frequently Half the Time Occasionally Almost Never Does Not Apply**

**Comments (optional):**

## TOUCH Processing

My child...

**16. shows distress during grooming (for example, fights or cries during haircutting, face washing, fingernail cutting)**

**Almost Always Frequently Half the Time Occasionally Almost Never Does Not Apply**

**17. becomes irritated by wearing shoes or socks**

**Almost Always Frequently Half the Time Occasionally Almost Never Does Not Apply**

**18. shows an emotional or aggressive response to being touched**

**Almost Always Frequently Half the Time Occasionally Almost Never Does Not Apply**

**19. becomes anxious when standing close to others (for example, in a line)**

**Almost Always Frequently Half the Time Occasionally Almost Never Does Not Apply**

**20. rubs or scratches a part of the body that has been touched**

**Almost Always Frequently Half the Time Occasionally Almost Never Does Not Apply**

**21. touches people or objects to the point of annoying others**

**Almost Always Frequently Half the Time Occasionally Almost Never Does Not Apply**

**22. displays need to touch toys, surfaces, or textures (for example, wants to get the feeling of everything)**

**Almost Always Frequently Half the Time Occasionally Almost Never Does Not Apply**

**23. seems unaware of pain**

**Almost Always Frequently Half the Time Occasionally Almost Never Does Not Apply**

**24. seems unaware of temperature changes**

**Almost Always Frequently Half the Time Occasionally Almost Never Does Not Apply**

**25. touches people and objects more than same-aged children**

**Almost Always Frequently Half the Time Occasionally Almost Never Does Not Apply**

**26. seems oblivious to messy hands or face**

**Almost Always Frequently Half the Time Occasionally Almost Never Does Not Apply**

**Comments (optional):**

## MOVEMENT Processing

My child...

**27. pursues movement to the point it interferes with daily routines (for example, can't sit still, fidgets)**

Almost Always Frequently    Half the Time    Occasionally    Almost Never    Does Not Apply

**28. rocks in chair, on floor, or while standing**

Almost Always Frequently    Half the Time    Occasionally    Almost Never    Does Not Apply

**29. hesitates going up or down curbs or steps (for example, is cautious, stops before moving)**

Almost Always Frequently    Half the Time    Occasionally    Almost Never    Does Not Apply

**30. becomes excited during movement tasks**

Almost Always Frequently    Half the Time    Occasionally    Almost Never    Does Not Apply

**31. takes movement or climbing risks that are unsafe**

Almost Always Frequently    Half the Time    Occasionally    Almost Never    Does Not Apply

**32. looks for opportunities to fall with no regard for own safety (for example, falls down on purpose)**

Almost Always Frequently    Half the Time    Occasionally    Almost Never    Does Not Apply

**33. loses balance unexpectedly when walking on an uneven surface**

Almost Always Frequently    Half the Time    Occasionally    Almost Never    Does Not Apply

**34. bumps into things, failing to notice objects or people in the way**

**Almost Always Frequently    Half the Time    Occasionally    Almost Never    Does Not Apply**

**Comments (optional):**

**BODY POSITION Processing**

**My child...**

**35. moves stiffly**

**Almost Always Frequently Half the Time Occasionally Almost Never Does Not Apply**

**36. becomes tired easily, especially when standing or holding the body in one position**

**Almost Always Frequently Half the Time Occasionally Almost Never Does Not Apply**

**37. seems to have weak muscles**

**Almost Always Frequently Half the Time Occasionally Almost Never Does Not Apply**

**38. props to support self (for example, holds head in hands, leans against a wall)**

**Almost Always Frequently Half the Time Occasionally Almost Never Does Not Apply**

**39. clings to objects, walls, or banisters more than same-aged children**

**Almost Always Frequently Half the Time Occasionally Almost Never Does Not Apply**

**40. walks loudly as if feet are heavy**

**Almost Always Frequently Half the Time Occasionally Almost Never Does Not Apply**

**41. drapes self over furniture or on other people**

**Almost Always Frequently Half the Time Occasionally Almost Never Does Not Apply**

**42. needs heavy blankets to sleep**

**Almost Always Frequently Half the Time Occasionally Almost Never Does Not Apply**

**Comments (optional):**

## ORAL SENSORY Processing

My child...

**43. gags easily from certain food textures or food utensils in mouth**

Almost Always Frequently    Half the Time    Occasionally    Almost Never    Does Not Apply

**44. rejects certain tastes or food smells that are typically part of children's diets**

Almost Always Frequently    Half the Time    Occasionally    Almost Never    Does Not Apply

**45. eats only certain tastes (for example, sweet, salty)**

Almost Always Frequently    Half the Time    Occasionally    Almost Never    Does Not Apply

**46. limits self to certain food textures**

Almost Always Frequently    Half the Time    Occasionally    Almost Never    Does Not Apply

**47. is a picky eater, especially about food textures**

Almost Always Frequently    Half the Time    Occasionally    Almost Never    Does Not Apply

**48. smells nonfood objects**

Almost Always Frequently    Half the Time    Occasionally    Almost Never    Does Not Apply

**49. shows a strong preference for certain tastes**

Almost Always Frequently    Half the Time    Occasionally    Almost Never    Does Not Apply

**50. craves certain foods, tastes, or smells**

Almost Always Frequently    Half the Time    Occasionally    Almost Never    Does Not Apply

**51. puts objects in mouth (for example, pencil, hands)**

**Almost Always Frequently    Half the Time    Occasionally    Almost Never    Does Not Apply**

**52. bites tongue or lips more than same-aged children**

**Almost Always Frequently    Half the Time    Occasionally    Almost Never    Does Not Apply**

**Comments (optional):**

**CONDUCT associated with sensory processing**

**My child...**

**53. seems accident-prone**

**Almost Always Frequently Half the Time Occasionally Almost Never Does Not Apply**

**54. rushes through coloring, writing, or drawing**

**Almost Always Frequently Half the Time Occasionally Almost Never Does Not Apply**

**55. takes excessive risks (for example, climbs high into a tree, jumps off tall furniture) that compromise own safety**

**Almost Always Frequently Half the Time Occasionally Almost Never Does Not Apply**

**56. seems more active than same-aged children**

**Almost Always Frequently Half the Time Occasionally Almost Never Does Not Apply**

**57. does things in a harder way than is needed (for example, wastes time, moves slowly)**

**Almost Always Frequently Half the Time Occasionally Almost Never Does Not Apply**

**58. can be stubborn and uncooperative**

**Almost Always Frequently Half the Time Occasionally Almost Never Does Not Apply**

**59. has temper tantrums**

**Almost Always Frequently Half the Time Occasionally Almost Never Does Not Apply**

**60. appears to enjoy falling**

**Almost Always Frequently Half the Time Occasionally Almost Never Does Not Apply**

- 
- 
- 
- 
- 
- 

**61. resists eye contact from me or others**

**Almost Always Frequently    Half the Time    Occasionally    Almost Never    Does Not Apply**

- 
- 
- 
- 
- 
- 

**Comments (optional):**

**SOCIAL EMOTIONAL responses associated with sensory processing**

**My child...**

**62. seems to have low self-esteem (for example, difficulty liking self)**

**Almost Always Frequently Half the Time Occasionally Almost Never Does Not Apply**

**63. needs positive support to return to challenging situations**

**Almost Always Frequently Half the Time Occasionally Almost Never Does Not Apply**

**64. is sensitive to criticisms**

**Almost Always Frequently Half the Time Occasionally Almost Never Does Not Apply**

**65. has definite, predictable fears**

**Almost Always Frequently Half the Time Occasionally Almost Never Does Not Apply**

**66. expresses feeling like a failure**

**Almost Always Frequently Half the Time Occasionally Almost Never Does Not Apply**

**67. is too serious**

**Almost Always Frequently Half the Time Occasionally Almost Never Does Not Apply**

**68. has strong emotional outbursts when unable to complete a task**

**Almost Always Frequently Half the Time Occasionally Almost Never Does Not Apply**

**69. struggles to interpret body language or facial expression**

**Almost Always Frequently Half the Time Occasionally Almost Never Does Not Apply**

**70. gets frustrated easily**

**Almost Always Frequently Half the Time Occasionally Almost Never Does Not Apply**

**71. has fears that interfere with daily routines**

**Almost Always Frequently Half the Time Occasionally Almost Never Does Not Apply**

**72. is distressed by changes in plans, routines, or expectations**

**Almost Always Frequently Half the Time Occasionally Almost Never Does Not Apply**

**73. needs more protection from life than same-aged children (for example, defenseless physically or emotionally)**

**Almost Always Frequently Half the Time Occasionally Almost Never Does Not Apply**

**74. interacts or participates in groups less than same-aged children**

**Almost Always Frequently Half the Time Occasionally Almost Never Does Not Apply**

**75. has difficulty with friendships (for example, making or keeping friends)**

**Almost Always Frequently Half the Time Occasionally Almost Never Does Not Apply**

**Comments (optional):**

**ATTENTIONAL responses associated with sensory processing**

My child...

**76. misses eye contact with me during everyday interactions**

Almost Always Frequently Half the Time Occasionally Almost Never Does Not Apply

**77. struggles to pay attention**

Almost Always Frequently Half the Time Occasionally Almost Never Does Not Apply

**78. looks away from tasks to notice all actions in the room**

Almost Always Frequently Half the Time Occasionally Almost Never Does Not Apply

**79. seems oblivious within an active environment (for example, unaware of activity)**

Almost Always Frequently Half the Time Occasionally Almost Never Does Not Apply

**80. stares intensively at objects**

Almost Always Frequently Half the Time Occasionally Almost Never Does Not Apply

**81. stares intensively at people**

Almost Always Frequently Half the Time Occasionally Almost Never Does Not Apply

**82. watches everyone when they move around the room**

Almost Always Frequently Half the Time Occasionally Almost Never Does Not Apply

**83. jumps from one thing to another so that it interferes with activities**

Almost Always Frequently Half the Time Occasionally Almost Never Does Not Apply

**84. gets lost easily**

**Almost Always Frequently    Half the Time    Occasionally    Almost Never    Does Not Apply**

**85. has a hard time finding objects in competing backgrounds (for example, shoes in a messy room, pencil in "junk drawer")**

**Almost Always Frequently    Half the Time    Occasionally    Almost Never    Does Not Apply**

**86. seems unaware when people come into the room**

[figure not shown]
**Almost Always Frequently    Half the Time    Occasionally    Almost Never    Does Not Apply**

**Comments (optional):**

Appendix B

Visual Analogue Scale – P.I.E.L Survey

[figure not shown]
## Appendix C

# Parent Handout

[figure not shown]
### Sensory Processing

Sensory processing refers to gathering sensory information from the environment through sensory receptors (ears, eyes, nose, mouth, skin and muscle), interpreting this information with stored memories and generating a response. The response will either be a desirable or undesirable behaviour depending on your child's sensitivities and arousal level.

#### Sensory processing steps:

#### Example:

[figure not shown]
## Arousal Levels

Children without sensory processing difficulties spend most of their day within an optimal level of arousal (illustrated by black line below). These children may briefly enter high or low arousal during the day but they are able to adapt and return to an optimal level of arousal with ease.

## High Arousal / Sensory Over-responsiveness

Children who are over-responsive to sensory stimuli spend most of their day in high arousal (illustrated by purple line below). When they are in high arousal they are unable to accurately register and interpret sensory information and exhibit sensitivity behaviours.

## Visual representation of arousal levels:

## Is my child entering high arousal?

You can anticipate when your child is entering high arousal by understanding the triggers to the behaviour and your child's body language and facial expressions. Every child has different triggers and will show different signs. Watch your child closely and take note of any environmental triggers that occur prior to the undesirable behaviour.

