The researcher and parent will identify a target undesirable behaviour (that is a result of sensory over-responsiveness) from a sensory domain of SP-2 where the child responded 'much more than others'. For example, if the child scores 'much more than others' in the area of touch, the researcher will refer to the 'almost always' and 'frequently' answers for the questions asked about touch. This will show what behaviours, related to sensory touch, are impacting the most on the the child and their family's day to day lives. Using the touch example, a target behaviour deduced from the SP-2 may be 'shows an emotional or aggressive response to being touched'. The impact (e.g. level of aggression from touch) of the target behaviour will be rated by the parent daily during the research period.

SCD research requires ongoing monitoring to effectively track individual outcomes (Mesibov & Shea, 2011). A Visual Analogue Scale (VAS) will be used to track the child's behaviour throughout the research period. Please see appendix B for copy for VAS. The VAS is the chosen instrument because it is individualised, user friendly, inexpensive and has good reliability and construct validity (Chafouleas, Sanetti, Kilgus, & Maggin, 2012; Wewers & Lowe, 1990). The VAS will be individualised for each participant, for example, using the behaviour defined above, the VAS would record parent daily perceptions from 'no aggression to 'high aggression'. To ensure consistency in the recognition of the target behaviour, the same parent will score the behaviour throughout the research period and a clear description of the behaviour will be provided on each VAS. Each night, parents will be required to 1) indicate whether the child presents the undesirable behaviour that day, and 2) mark on a line how they perceived the impact of the target behaviour that day. To make rating accessible and efficient, parents will use the application P.I.E.L. Survey (Jessup, Bian, Chen, & Bundy, 2012) where they will be able to access their individualised VAS each day. The parents will be able to loan an iPod touch from The University of Sydney if they do not have own a compatible iOS device. Using P.I.E.L. Survey allows the researchers to download all the participant's responses. By utilising a VAS, a parent-rated assessment measure, the effects of the researcher also being the interventionalist are minimised.

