The design of this SCD research study mimics real life therapy strategies whereby parents implement intervention throughout the day with their child. However, to analyse a causal relationship between the intervention and the undesirable behaviours, evaluation at the end of each day which encompasses the parent's perceptions of their child's behaviour throughout the day is included.

**Intervention:** In line SCD research, the intervention has been developed to reflect real world occupational therapy with an aim of being easily embedded into regular routines, with minimal additional demands for participants. Furthermore, each participant is able to work towards an outcome meaningful to them. Each child has their own target behaviour which is measured using the VAS and their own set of proprioceptive activities that work for their family. However, important to the research design is the consistency of proprioceptive input being received by the child in the set activities (Mesibov, 2011). Therefore, to ensure each child is correctly receiving proprioceptive input, the intervention phase includes: education, programming, modelling and follow up.

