Education will involve the researcher (occupational therapist) explaining the fundamentals of sensory over-responsiveness to parents and how to be responsive through understanding the signs of over-responsiveness and triggers for the child's target behaviour. The researcher will work with the parent to develop a program of activities that primarily provide proprioceptive input to the body. These activities will be those that can easily be implemented in the home environment and in the child's established routine, typically embedded within play or jobs around the house. The recommended activities do not involve expensive equipment or specialised training to administer. The parent will facilitate the proprioceptive activities when triggers of the target behaviour are present or when they observe the child showing signs of over-responsiveness. Please see appendix C for parent handout. The researcher will model how to engage the child in these activities and how to perform the activities correctly in order to provide proprioceptive input. The parent will facilitate the activities for 10-15 minutes, or until they see a positive change in the child's face and body language. This time frame was chosen as it is a commonly used time frame for implementing sensory based intervention (e.g. Bagatell et al., 2010; Escalona et al., 2001; Reichow et al., 2010; Schilling & Schwartz, 2004; Silva et al., 2009). The researcher will visit the home weekly during the intervention 'B' phase, ideally when the target behaviour is expected to occur, to follow up and provide further guidance to the parents.

Due to the target behaviour being a behaviour scored as 'always' or 'frequently' on the SP-2, it is anticipated the behaviour will occur almost, if not, daily and may even occur numerous times a day. It is not anticipated that the intervention will remove the behaviour altogether, but rather, from being responsive to the child's signs of entering high arousal and becoming over-responsive to certain sensory stimuli, the perceived impact of undesirable behaviour will be minimised.

**Expected duration of study:** The research period for each participant is 9 weeks. The total length of the study will be from July 2017 to July 2018.

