## Individual Family Plan

**Target Behaviour** (*child's individual factors will be added*):

What time does the behaviour generally occur?	What are the environmental / external triggers?	What are the child's body language / facial expressions before the behaviour / entering high arousal?
e.g. morning (9-11am) and afternoon (2-5pm)	e.g. lawn mower, vacuum, traffic, non-desired activity, other person touching	e.g. stiff movements, moving away, decreased eye contact, increased heart rate, faster breathing

**Activities** (*activities that are not appropriate to the family will be deleted*):

Body	Legs, feet	Arms, hands	Mouth

Child Burrito:
 
Roll child in sheets, add "ingredients to burrito" (deep pushes) and have them try to get themselves out
	
Child Sandwich:
 
Sandwich the child's legs between cushions, have them try to get themselves out
	
Hug:
 
Hug the child tightly. Have them try to get themselves free by pushing out with their arms
	
Chewing:
 
Provide your child with a chewy necklace or chewy foods (dried fruit, gum)

Animal crawls:
 
Have the child get on all fours and crawl like a dog, cat, bear, monkey or any animal of your choice. Add a something weighted on their back to make it a turtle crawl
	
Chair elastic:
 
Put elastic (or theraband) around the chair legs. Have child push their feet / ankles against it when seated
	
Playdough:
 
Have the child roll, squeeze, pinch and flatten playdough (or theraputty)
	
Sucking:
 
Have your child suck their drink through a thin and/or curly straw (or thicker liquid e.g. yogurt through a straw)

Obstacle course:
	
Leg press:
 
Have child lay out their back. Place
	
Squeeze toy :
 
Provide your child with a squeeze toy that has some
	
Crunching:
 
Have your child eat crunchy food such

Have your child crawl over, under and through furniture	cushion on their feet and have them push it up	resistance – could use a home-made stress ball with balloons and flour.	as carrot or celery sticks or have them crunch down on ice

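### The parent who does all the rating is first told to watch closely in the Phase B training, so an A1-to-B change in VAS level may partly reflect changed observation

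*Protocol*

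**What the plan says.** Section 6 (Procedure and measures) bases consistent measurement on two constants: "the same parent will score the behaviour throughout the research period and a clear description of the behaviour will be provided on each VAS". This parent reports nightly whether the behaviour occurred and then has to "mark on a line how they perceived the impact of the target behaviour that day".

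The same parent delivers the intervention after training. Section 6 (Intervention) states that "the intervention phase includes: education, programming, modelling and follow up", and that the education covers "how to be responsive through understanding the signs of over-responsiveness and triggers" of the child's target behaviour. In the Section 10 timeline the Phase B row lists "Provide education to family (see handout below" and creation of the family plan as researcher tasks. The A1 row gives the parent daily scoring only, with no home visits except for help with the app. The A2 row has a reminder to stop the proprioceptive intervention and says nothing about watching.

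Appendix C contains the instruction itself: "Watch your child closely and take note of any environmental triggers that occur prior to the undesirable behaviour". Lists of triggers and bodily signs follow. The Individual Family Plan then asks, among other things, "What time does the behaviour generally occur".

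**The concern.** Keeping the rater and the wording constant does not keep constant how hard the rater looks. Both nightly items depend on what the parent noticed that day. On the visible text, close watching is first requested during Phase B, in the same training that starts the activities. A change in the measuring process therefore coincides with the A1-to-B contrast, where Section 6 (Data analysis) judges change in level and immediacy of effect.

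Section 6 argues that a parent-rated scale reduces the effect of the researcher also being the therapist. That deals with the researcher's dual role. It does not deal with the parent's, who is both sole rater and deliverer. At stake is whether an A1-to-B change can be credited to proprioceptive input, which is what the research question and the planned conclusion name.

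**Working it through.** **Step 1. Phase lengths (Section 10 dates, counted inclusively).** A1, 14 to 27 August: 14 days. B, 28 August to 1 October: 35 days. A2, 2 to 15 October: 14 days. 14 + 35 + 14 = 63 days, and 63/7 = 9 weeks, which agrees with the stated research period.

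**Step 2. Share of B affected.** The timeline fixes no day for the education. Assume that it happens at the first weekly visit, on day k = 1 to 7 of B. The share of B days on or after it is (35 − k + 1)/35: 35/35 = 100% for k = 1, 32/35 = 91% for k = 4, and 29/35 = 83% for k = 7. Most of B is affected, but the switch need not fall on the boundary itself.

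**Step 3. Effect on the planned contrasts.** Let t be the true effect of the activities in B (negative is better) and s the shift in ratings from changed observation. For simplicity both apply to all of B. The protocol gives no VAS values, so t and s, in mm, are assumptions.

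- B − A1 = t + s in either case.
- If the shift persists in A2: A2 − B = −t and A2 − A1 = s.
- If the shift fades in A2: A2 − B = −(t + s) and A2 − A1 = 0.

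| s | t | B − A1 | A2 − B, persists | A2 − A1, persists | A2 − B, fades | A2 − A1, fades |
|---|---|---|---|---|---|---|
| −10 | 0 | −10 | 0 | −10 | +10 | 0 |
| −10 | −15 | −25 | +15 | −10 | +25 | 0 |
| −5 | 0 | −5 | 0 | −5 | +5 | 0 |
| −5 | −15 | −20 | +15 | −5 | +20 | 0 |
| +5 | 0 | +5 | 0 | +5 | −5 | 0 |
| +5 | −15 | −10 | +15 | +5 | +10 | 0 |
| +10 | 0 | +10 | 0 | +10 | −10 | 0 |
| +10 | −15 | −5 | +15 | +10 | +5 | 0 |

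With no true effect and a fading shift of −10, the series falls by 10 and then rises by 10, which looks like a treatment reversal. With a true fall of 15 and s = +10, only 5 mm shows from A1 to B.

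**Step 4. Direction.** Assume, for illustration, that the parent notices 60% to 80% of episodes in A1 and 90% in B.

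- If the rating follows the number noticed, it changes by 0.9/p − 1: +50% at p = 0.6 and +12.5% at p = 0.8.
- If it follows average severity, and newly noticed episodes are half as severe, it changes by (p + 0.5(0.9 − p))/0.9 − 1: −16.7% at p = 0.6 and −5.6% at p = 0.8.

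The sign depends on how the parent forms the rating, which the protocol does not settle. These figures show only that either direction is possible. They do not estimate a bias.

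**The case against.** The handout sentence concerns triggers and serves to time the activities. It does not mention rating, and it changes neither the scale nor the description. Nor is A1 an unwatched phase. The parent has already completed the SP-2, which names many of the same triggers, has helped choose a behaviour that is frequent and has a strong impact on the family, and must report nightly whether it occurred. Such a behaviour may seldom be missed. The VAS screens in Appendix B are not shown and the consent material was removed, so an A1 observation instruction could exist there. All of this stands, and it makes the shift possible rather than demonstrated. It does not remove the asymmetry: a parent told to look for what precedes an episode is also better placed to notice the episode.

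The planned analysis also gives some protection, because B is compared with A2 and A1 with A2. This protection is partial. It works for B-to-A2 only if the shift persists, and the resulting A1–A2 difference could equally be carry-over from the intervention. Section 6 concedes that an ABA design falls short of the recommended three demonstrations of effect, so there is little redundancy.

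A reader might go further and infer that observation effort switches exactly at the boundary, that A1 is not comparable with B, or that visual analysis can never separate the two explanations. The documents do not support these readings. The handout says nothing about starting, and its timing comes from the timeline, which gives no day. Daily rating against a fixed description runs through every phase. A lasting shift would also leave a visible trace in A1 versus A2.

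Finally, education is a declared part of the intervention. That limits what may be attributed to the activities alone, but a change in what the rater detects is still a measurement effect.

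**Conclusion.** The point holds as a measurement caveat that should be dealt with before A1 starts. Training of the only rater, who also delivers the activities, coincides with Phase B, and the plan does not hold the observation instruction constant. An A1-to-B change may therefore mix the effect of the activities with changed observation.

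Size and direction are unknown. Any shift s enters A1-to-B in full if it is present throughout B, and still affects 83% to 100% of B days if education falls in the first week. Whether it also distorts B-to-A2 depends on whether it fades after the activities stop. The conclusion rests on the visible text, in which A1 has no equivalent instruction. It does not show that the ratings are in fact biased or that the ABA comparison is invalid.

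**What to change.** - At the existing home visit or survey set-up before A1 (Sections 7 and 10), give every parent one standard instruction: watch for the target behaviour throughout the day and rate it in the same way on all 63 days.
- State in Section 6 (Procedure and measures) that this instruction is identical in A1, B and A2, and repeat it at the start of B and of A2.
- Keep the teaching on triggers, signs and activities in Phase B. Moving it before A1 would equalise the parent's knowledge, but it would also place a declared component of the intervention in the baseline, where it could change behaviour.
- State in Section 6 (Data analysis) that an A1-to-B change reflects the education-plus-activity package, not proprioceptive input alone.

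The cost is a short script and a few sentences of protocol text, with no added visit, staff or participants. Closer watching in A1 may slightly alter baseline ratings, but the instruction then applies equally in every phase. The fix reduces the asymmetry without wholly removing it, because the Phase B training may still sharpen the parent's attention.
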